### 10.3. Assignment of Adverse Event Intensity and Relationship to Investigational Product

All adverse events, including those that are serious, will be graded according to the National Cancer CTCAE version 4.0. The following categories and definitions of causal relationship to study drug as determined by a physician should be used for all BMS clinical study AEs:

- Related: There is a reasonable causal relationship to study drug administration and the AE
- Not related: There is not a reasonable causal relationship to study drug administration and the AE

The expression "reasonable causal relationship" is meant to convey in general that there are facts (e.g. evidence such as de-challenge/re-challenge) or other arguments to suggest a positive causal relationship.

### 10.4. Collection and Reporting

Adverse events can be spontaneously reported or elicited during open-ended questioning, examination, or evaluation of a subject. (In order to prevent reporting bias, patients should not be questioned regarding the specific occurrence of one or more AEs.) If known, the diagnosis of the underlying illness or disorder should be recorded, rather than its individual symptoms. The following information should be captured for all AEs: onset, duration, intensity, seriousness, relationship to study drug, action taken, and treatment required. If treatment for the AE was administered, it should be recorded on the appropriate CRF page. The investigator shall supply the IRB with any additional requested information, notably for reported deaths of patients. Completion of supplemental CRFs may be requested for AEs and/or laboratory abnormalities that are reported/identified during the course of the study.

#### 10.4.1. Serious Adverse Events

Following the subject's written consent to participate in the study, all SAEs must be collected, including those thought to be associated with protocol-specified procedures. All SAEs must be collected that occur within 14 days of discontinuation of dosing of the study drug. If applicable, SAEs must be collected that relate to any later protocol specified procedure. The investigator will notify the local IRB of any SAE occurring after this time period that is believed to be related to the study drug or protocol-specified procedure. Serious adverse events, whether related or unrelated to study drug, must be reported within local regulatory requirements. An SAE report should be completed for any event where doubt exists regarding its status of seriousness.

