## **Brief Study Synopsis**

**Study Phase:** Pilot

**Primary hypothesis:** Pentoxyfylline (PTX) therapy at 1200 mg per day or the renally dose equivalent in addition to standard of care is superior to placebo in the treatment of acute renal failure (ARF) not responsive to volume resuscitation in hospitalized patients with cirrhosis.

**Study design:** Prospective, placebo-controlled, randomized pilot trial.

Each hospitalized subject will undergo pre-dosing screening with review of his or her history and physical exam from the day of enrollment and safety assessment to ensure no contraindication to use of PTX.

ARF will be defined according to the definition put forth by and validated prospectively by collaboration between the International Ascites Club (IAC) and the Acute Dialysis Quality Initiative as a rise in creatinine of 0.3 mg/dl or 50% from baseline creatinine, which will be defined as the most recent stable measurement before admission.[1]

Baseline testing will be obtained from hospitalization records, including but not limited to chemistry panel, liver function testing, urinalysis, urine electrolytes, coagulation studies, blood cultures, chest x-ray, diagnostic paracentesis, abdominal ultrasound with Doppler.

Subjects will take either placebo three times a day or PTX 400mg three times a day or 400mg twice a day for eGFR 10-50 and 400mg once a day for eGFR <10 for 14 days in addition to standard inpatient care. Treatment will be continued for 14 days unless a study endpoint has been reached at which time either PTX or placebo will be stopped.

**Total study subjects expected:** 30 patients with cirrhosis hospitalized ARF

**Duration of study:** 180 days

**Study Drugs:** PTX 400 mg tablets and placebo. The study team will not be pursuing a change in labeling or an FDA approved indication for this drug as a part of this proposal. Standard placebo provided in similar tablet forms. All investigational drugs will be prepared by the Investigational Pharmacy by inserting the active drug/placebo into larger cloaking capsules. Standard corn starch will be used inside the placebo capsule.

Randomization will be 1:1. The Investigational Pharmacy will be performing randomization and will generate the block randomization scheme.

**Endpoints:** The primary endpoint is resolution of ARF, defined as a return to baseline creatinine for 24 hours.

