## 2. Study Design

[figure not shown]
The proposed study is a blinded prospective, placebo controlled, randomized pilot study. Figure 1 shows the study design schematic. Subjects will be identified during their hospitalization with ARF. Each subject will undergo screening and a pre-dosing history and physical exam, and safety assessment, which will include reviewing basic blood work results and imaging from their hospitalization (CBC, CMP, INR, Blood cultures, UA and urine culture, Urine lytes, Chest x-ray, Abdominal ultrasound with dopplers, diagnostic paracentesis if ascites is present) and performing urine pregnancy testing in women of child bearing potential. Subjects will be randomized 1:1 by the Investigational Pharmacy.

Subjects will then take a 14-day course of PTX 400 mg three times a day. On day 3 there will be an in-person assessment and review of side effect profile. If there have been no serious adverse events, PTX will be continued. Additional safety assessments will be completed at day 7,10,14.

Patients will also be seen in the hospital to assess for treatment response at day 3,7,10,14. At these visits, they will have repeat blood work at the discretion of the treating physicians (e.g. CBC, CMP, INR, UA with reflex urine culture, Urine lytes,). During each assessment, primary and secondary endpoints will be measured. If an endpoint is obtained, the patient will be instructed to stop therapy.

Survival will be assessed at 30 and 180 days by telephone interviews. If subjects are discharged prior to completing 14 days of therapy, they most likely has met an endpoint (resolution, death, transplant, etc). If in the unlikely event the patient is to be discharged and they have not met an endpoint, they will be withdrawn from the study. Once the patient is discharged there will be no in person follow up evaluations.

Figure 1: Study protocol

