### 7.2. Study Drug Discontinuation

Study drug or placebo will be discontinued if a grade 3 adverse event (based on the NCI Common Terminology Criteria for Adverse Events, CTCAE, version 4.0) related to the study drug at the judgment of the PI and medical monitor. The PI will notify the medical monitor of a grade 3 adverse event over the phone and the medical monitor will conduct an independent review with access to the medical record. The medical monitor may interview the patient at the bedside should they deem this necessary. Meetings between the medical monitor and the PI will take place on an as needed basis. One scheduled meeting will take place after 50% enrollment has been completed to review all the reported adverse events.

Study drug or placebo will be discontinued if a grade 4 adverse event or pregnancy occurs during the study protocol or at the request of the subject. If the subject misses a dose and is less than 4 hours late, the subject will be advised to make up the dose. Otherwise, the dose can be omitted and per protocol dosing can resume with the next scheduled administration.

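### The SAE collection window ends 14 days after a last dose that depends on outcome, so raw non-fatal SAE counts may be modestly biased, in either direction, if stop times differ by arm

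*Combined protocol and SAP*

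**What the plan says.** Section 10.4.1 opens the SAE window at consent ("Following the subject's written consent to participate in the study, all SAEs must be collected") and closes it relative to the last dose ("All SAEs must be collected that occur within 14 days of discontinuation of dosing of the study drug"). After that, reporting narrows to events judged related to the drug or to a protocol procedure, in these words: "The investigator will notify the local IRB of any SAE occurring after this time period that is believed to be related to the study drug".

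The date of the last dose varies between patients. The Brief Study Synopsis says "Treatment will be continued for 14 days unless a study endpoint has been reached at which time either PTX or placebo will be stopped". Section 2 measures primary and secondary endpoints at each assessment and adds "If an endpoint is obtained, the patient will be instructed to stop therapy". Its response visits are set by "Patients will also be seen in the hospital to assess for treatment response at day 3,7,10,14". Section 7.2 stops drug for a related grade 3 event, and further: "Study drug or placebo will be discontinued if a grade 4 adverse event or pregnancy occurs". The patient may also ask to stop. Stops under section 7.2 are not tied to a visit.

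Safety is part of the primary objective in section 5.1. Section 9 specifies no SAE comparison by arm, and no section gives a fixed-day SAE cut-off or an exposure-adjusted SAE rate.

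**The concern.** Time under SAE observation is decided after randomisation, partly by the outcome that treatment is meant to change. The primary endpoint itself ends dosing: "The primary endpoint is resolution of ARF, defined as a return to baseline creatinine for 24 hours". If one arm stops drug earlier than the other, that arm has fewer days in which any SAE, related or not, is recorded. An unrelated SAE on day 20 is collected in a patient who completed the course and need not be collected in one who stopped on day 3.

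What is at stake is the descriptive safety evidence. No formal safety test is planned, so the SAE counts in the two arms carry much of the weight for the safety half of the primary objective. Complete ascertainment inside each patient's window would not cure a difference in window length.

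**Working it through.** The plan states no SAE rate and no total window length, so there is no figure to reproduce. The window lengths below follow from the plan. The bias figures rest on assumptions.

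**Window length.** Inputs: 14 days after the last dose (section 10.4.1), a planned course of 14 days (Synopsis), and response visits on days 3, 7, 10 and 14 (section 2).

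Window end = stop day + 14. Shortfall against a full course = (14 + 14) − (stop day + 14) = 14 − stop day.

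| Stop day | Window ends | Days lost | Share of full window |
|---|---|---|---|
| 1 (toxicity or request) | 15 | 13 | 54% |
| 2 (toxicity or request) | 16 | 12 | 57% |
| 3 (first response visit) | 17 | 11 | 61% |
| 7 | 21 | 7 | 75% |
| 10 | 24 | 4 | 86% |
| 14 (full course) | 28 | 0 | 100% |

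**Effect on counts.** Assumptions: no true drug effect on SAEs; a constant hazard h, the same in every patient; 28-day SAE risk R of 20%, 40% or 60%; 15 patients per arm (section 9).

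h = −ln(1 − R)/28. Recorded risk in an arm = sum over stop days of (share stopping that day) × (1 − exp(−h × (stop day + 14))).

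Worked case, R = 40%: h = 0.5108/28 = 0.01824 per day. Recorded risk is 26.7% for a 17-day window, 31.8% for 21 days, 35.5% for 24 days and 40.0% for 28 days. Suppose that 60% of one arm and 20% of the other resolve early, spread equally over days 3, 7 and 10.

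- 60% arm: 0.20 × (0.267 + 0.318 + 0.355) + 0.40 × 0.400 = 0.348; mean window 23.6 days.
- 20% arm: 0.0667 × (0.267 + 0.318 + 0.355) + 0.80 × 0.400 = 0.383; mean window 26.5 days.
- Difference: 3.5 percentage points, or 0.52 patients of 15.

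Shift in the expected number of patients with a recorded SAE, out of 15:

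| Early stops, arm A v arm B | R = 20% | R = 40% | R = 60% |
|---|---|---|---|
| 30% v 30%, days 3/7/10 | 0 | 0 | 0 |
| 20% v 40%, days 3/7/10 | 0.15 | 0.26 | 0.33 |
| 20% v 60%, days 3/7/10 | 0.29 | 0.52 | 0.66 |
| 20% v 60%, all on day 3 | 0.44 | 0.80 | 1.04 |
| Bound: 0% v 100%, all on day 3 | 1.1 | 2.0 | 2.6 |

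The arm with more early stops always shows the lower count. Exchanging the arms reverses the sign and leaves the size unchanged. The last row marks the limit of the effect and is not a plausible scenario.

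**Sensitivity to the constant hazard.** Take 2% per day throughout, with 60% v 30% stopping on day 5 (window 19 days). Recorded risks are 0.6 × 0.316 + 0.4 × 0.429 = 36.1% against 0.3 × 0.316 + 0.7 × 0.429 = 39.5%, a shift of 0.5 patients. If the hazard falls to 1% per day after day 14, the same case gives 30.6% v 32.4%, or 0.3 patients. A risk concentrated in the acute phase therefore shrinks the effect.

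**After a fixed window.** Every patient has the same window, so the difference due to window length alone is zero at every assumed rate.

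**The case against.** The case against acting is that this is a 30-patient pilot with no planned SAE test, that the loss is narrow, and that other provisions limit it.

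- Survival is assessed at days 30 and 180 in both arms (sections 2 and 8.2), so deaths are not lost.
- Section 10.4.2 requires follow-up of non-serious events that interrupt or end dosing, and their reporting as SAEs if they become serious.
- Section 10.4.1 still brings in later SAEs believed related.

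All of this stands. What remains exposed is later non-fatal SAEs not judged related, and that judgement is itself a reason to want a common cut-off.

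Three stronger readings are tempting. A reader might infer that the rule must flatter PTX, because faster resolution shortens its window. The documents do not fix the direction: section 2 stops therapy at secondary as well as primary endpoints, and section 3 ends participation at transplant or renal replacement therapy. If placebo patients progress more often, placebo may have the shorter window.

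A reader might also infer that patients harmed by the drug escape the count. A toxicity that meets the SAE definition in section 10.2 already counts that patient, so it is mainly later or repeat events that are lost.

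Lastly, a reader might extend the point to the 25% hold rule in section 10.6. That rule pools the arms, so an imbalance between arms is not what it measures. At 1%, 2% and 3% per day, the recorded risks for 17-day and 28-day windows are 16% and 24%, 29% and 43%, and 40% and 57%. Each pair lies on one side of 25%.

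Exposure-adjusted rates are a fair alternative without longer collection. However, they assume a roughly constant hazard and stopping that is unrelated to later risk, and neither is assured here.

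**Conclusion.** The point holds as a modest, inexpensive improvement. That the window depends on the stop day, with 11 days lost at a day-3 stop and up to 13 at an earlier toxicity or request stop, follows directly from the text. Bias in the arm comparison is conditional: it needs stop times that differ by arm, and the plan gives no information on them. Under the assumed SAE risks and the non-extreme stopping patterns, the shift is about one patient of 15 or fewer.

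A reader might conclude that SAE counts in the two arms cannot be compared at all. The documents do not support that, since equal stop times give an expected difference of zero.

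The size rests on assumed SAE risks, stopping shares and a hazard common to all patients. If early resolvers have a lower SAE risk than others, the shift is smaller; if those who stop for toxicity have a higher risk, it is larger.

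**What to change.** In section 10.4.1, collect all SAEs, related or not, from consent to a fixed day 30 for every randomised patient, whatever the date of the last dose. Say explicitly that this includes patients who stop early, are discharged or are withdrawn. In Table 2, add an SAE query to the day-30 call, whose column now marks only ARF response. In section 9, state that SAEs will be summarised by arm on this window.

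Leave the section 10.6 hold rule as it is, and say that the day-30 summary does not alter it. Feeding the longer window into that rule could move its trigger: at 1% per day, 1 − exp(−0.01 × 30) = 25.9%, against 24% at 28 days.

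While editing Table 2, reconcile its day 14 and 28 column, which marks a safety assessment, with section 2, which lists safety assessments only to day 14 and no in-person follow-up after discharge.

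The cost is up to 30 − 15 = 15 more days of SAE collection for the earliest stoppers and 30 − 28 = 2 for those who complete, one extra question on a call already scheduled, and small edits to section 9 and Table 2. Dosing and stopping rules are untouched.

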## 8. Study Assessments

### 8.1. Schedule of Visits

The schedule of study assessments and visits is shown in Table 2.

Table 2: Schedule of visits and study protocol assessments

Visit	Screening initial assessment	Follow up assessment	"Partial response" assessment	Phone Call
Day	0	Day 3,7,10,14	Day 14, 28	Day 30,180
Initial history and physical exam	X			
ARF response assessment		X	X	X
Symptom triggered physical exam		X	X	
Interim safety assessment and pill count		X	X	
Labs and imaging	X	X	X	

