### 8.2. Primary Endpoints

ARF treatment response will be assessed according to Table 2. The PI or sub-investigators will perform all assessments and will assess for the presence of side effects or toxicities of the study drug by performing a brief history at each visit and by performing a targeted physical exam. A phone call to assess 30 and 180-day survival will be completed.

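### For discharged patients, no reconciled study contact asks about nonfatal SAEs in the required 14-day post-dose window, which weakens the safety objective and the 25% hold rule

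*Combined protocol and SAP*

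**What the plan says.** **The duty.** Section 10.4.1 starts collection at consent ("Following the subject's written consent to participate in the study, all SAEs must be collected") and carries it past the last dose: "All SAEs must be collected that occur within 14 days of discontinuation of dosing of the study drug".

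**When dosing stops.** Section 2 plans 14 days of treatment but stops it when an endpoint is reached. It expects a patient who leaves hospital before day 14 to have met an endpoint in most cases. A patient discharged without one is withdrawn. Section 3 also ends participation at death, liver transplant or renal replacement therapy (RRT).

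**Scheduled contacts.** After the day-3 assessment, Section 2 says "Additional safety assessments will be completed at day 7,10,14". Response is assessed in the hospital on the same days. On what follows discharge it says "Once the patient is discharged there will be no in person follow up evaluations".

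**The calls.** Section 2 says "Survival will be assessed at 30 and 180 days by telephone interviews", and Section 8.2 repeats the purpose: "A phone call to assess 30 and 180-day survival will be completed".

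**Table 2 (Section 8.1).** The row "Interim safety assessment and pill count" is marked for the follow-up assessments (days 3, 7, 10, 14) and for the partial-response assessment (days 14 and 28). It is blank for the phone calls (days 30 and 180), where only ARF response is marked.

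**Use of the SAE count.** Section 5.1 makes safety part of the primary objective. Section 10.6 puts enrollment on hold if SAEs occur in more than 25% of participants.

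**The concern.** A patient whose renal failure resolves stops the drug and may go home soon after. Most or all of that patient's 14-day post-dose window then falls after discharge, when Section 2 allows no visit and the only planned calls are not assigned a safety question. A site could follow the written schedule exactly and still fail the duty in Section 10.4.1 without knowing it.

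Section 10.2 counts inpatient hospitalization as an SAE, so a readmission during the window qualifies in itself. Such events would reach the study team only if someone volunteered them. Two things rest on the count: the safety half of the primary objective, and the only study-level rule for pausing enrollment.

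**Working it through.** The 14-day window is a rule, so there is no calculated figure to reproduce. The check has four steps.

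**1. When each window closes.** Close = last-dose day + 14.

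| Last dose | Window closes | Day-30 call after close? |
|---|---|---|
| Day 3 | 3 + 14 = 17 | yes |
| Day 7 | 7 + 14 = 21 | yes |
| Day 10 | 10 + 14 = 24 | yes |
| Day 14 | 14 + 14 = 28 | yes |

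**2. How much of the window falls after discharge.** Days after discharge = stop day + 14 − discharge day, with inpatient days treated as observed.

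- Discharged on the stop day: 14 of 14.
- Stop day 7, discharge day 10: 7 + 14 − 10 = 11 of 14 (79%).
- Stop day 14, discharge day 21: 14 + 14 − 21 = 7 of 14 (50%).
- Stop day 14, inpatient to day 28: 0 of 14.

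Under Section 2, none of these post-discharge days is covered by a visit. Under Table 2, the day-28 assessment could cover them, but that column also marks a physical exam and labs, which Section 2 excludes for a discharged patient. Its label also leaves unclear whether it applies to patients who have resolved. The two places cannot both be followed.

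**3. Effect on the hold rule.** 25% of 30 is 7.5, so more than 25% means 8 or more. If the true risk that a patient has an SAE is p, and a fraction c of those patients have it recorded, the chance of reaching the threshold is P(X ≥ 8), where X is binomial with n = 30 and probability p × c. The documents give neither p nor c, so both are assumed.

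| True risk p | c = 100% | c = 80% | c = 60% |
|---|---|---|---|
| 20% | 0.24 | 0.10 | 0.02 |
| 30% | 0.72 | 0.44 | 0.16 |
| 40% | 0.96 | 0.79 | 0.44 |
| 50% | 1.00 | 0.96 | 0.72 |

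This takes all 30 patients as the denominator. During accrual the denominator is smaller, but under-capture still lowers the chance of crossing 25%.

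**4. Effect between arms, only if discharge timing differs.** Assume the same true 14-day nonfatal SAE risk r in both arms, a constant hazard h = −ln(1 − r)/14, and no capture after discharge (the extreme case). With d inpatient days in the window, the observed risk is 1 − exp(−h × d).

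| r | d = 2 | d = 7 | False difference | Patients in 15 |
|---|---|---|---|---|
| 10% | 1.5% | 5.1% | 3.6 points | 0.5 |
| 20% | 3.1% | 10.6% | 7.4 points | 1.1 |
| 30% | 5.0% | 16.3% | 11.4 points | 1.7 |

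With d = 5 in both arms the difference is 0, and both arms are under-counted alike.

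**The case against.** The strongest reply is that the plan already contains what is needed. Table 2 schedules a safety-marked assessment on day 28, exactly when the longest window closes. Section 10.4 lets adverse events be reported spontaneously or found by open-ended questioning, and does not limit this to inpatients. Section 10.4.2 requires follow-up of nonserious events still present at the end of participation, and reporting as SAEs if they become serious. Section 8.2 says the investigators "will assess for the presence of side effects or toxicities of the study drug by performing a brief history at each visit", and Table 2 lists the calls under its visit heading. Death is an SAE by Section 10.2, so the day-30 call would find fatal events.

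Much of this stands. A reader might infer that nothing scheduled after day 14 asks about safety; the day-28 column shows that this is too broad. Deaths are also covered, so the gap concerns nonfatal SAEs.

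The reply does not close that gap. The day-28 assessment conflicts with Section 2 for anyone at home. Section 10.4 attaches its questioning to no post-discharge contact. Section 10.4.2 helps only with events already known. Reading the calls as visits under Section 8.2 is possible, but that section also calls for a targeted physical exam, and Table 2 leaves the calls' safety cell blank.

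A reader might also infer that SAEs will be under-counted most on pentoxifylline, so that it looks safer than it is. This is foreseeable if the drug speeds resolution and discharge. The documents do not establish it: they give no discharge times or SAE rates by arm. Withdrawal of patients discharged without an endpoint (Section 2) and the end of participation at transplant or RRT (Section 3) could lose events in the arm that does worse.

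**Conclusion.** The point holds in this form: Section 10.4.1 requires complete SAE collection for 14 days after the last dose, and for discharged patients no reconciled contact elicits the nonfatal events. Section 2 and the day-28 column of Table 2 contradict each other, and the day-30 call is not assigned the task.

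The consequence that needs no assumption about the arms is a weaker hold rule. At an assumed true SAE risk of 40%, 60% capture cuts the chance of reaching 8 of 30 from 0.96 to 0.44. The true risks and capture fractions are illustrative. Actual capture may be better, since inpatient events are seen and deaths are found at day 30.

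A bias between arms is conditional on different discharge timing, and its net direction cannot be read from the documents. The point should be corrected before enrollment. It does not show that the safety comparison is biased in favor of pentoxifylline.

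**What to change.** 1. Add one open-ended SAE question to the day-30 call, in keeping with the non-leading questioning required by Section 10.4, and a check of hospital readmission records since discharge.
2. Mark the safety row of Table 2 for day 30, and add SAE collection to the purpose of that call in Sections 2 and 8.2.
3. State that the call is also made to patients who were withdrawn and to those whose participation ended at transplant or RRT, unless they withdraw consent. Without this, the patients lost would be a selected group.
4. Reconcile the day-28 assessment in Table 2 with Section 2: say to whom it applies and what happens for a patient already discharged.

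No new contact is needed, because day 30 follows the close of every window. The cost is a few minutes per call and the weakness of recall-based reporting, which the record check partly offsets. The change does not equalize the length of observation, since each window still depends on when dosing stopped.
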